5.3 Treatment of patients

Table 5–1 List of products provided by Novo Nordisk

Compound Name	Strength	Dosage form	Route of administration	Treatment period
Concizumab B²,	100 mg/mL	3 mL solution in a 3 mL cartridge ³ .	S.c. administration using NovoPen [®] 4	For prophylactic treatment for 76 weeks.
Turoctocog alfa (NovoEight[®])⁴, Sodium chloride solution 4ml	2000 IU/vial	Powder for solution for injection Solvent for solution for i.v. injection used for reconstitution of turoctocog alfa.	I.v. administration	For treatment of breakthrough bleeding episodes (or prophylaxis in the screening and follow-up phases), at the discretion of the treating physician (patients may choose to use other familiar pre-trial FVIII drug). For further information see section 5.3.2

Concizumab will be given s.c., once daily for a total dosing period of 76 weeks.

The NovoPen[®]4 injector will be supplied by Novo Nordisk and used for the s.c. administration of concizumab. It will be labelled in accordance with national legislation and a copy of the label can be found within the Trial Materials Manual, see Section [9.1](#).

The first dose of concizumab will be given at the trial site under medical supervision. After the initial dose the patient must be observed for potential emergence of AEs/safety signals for at least 2 hours at the trial site. At the screening visit and the first scheduled treatment visit patients will be trained in s.c. administration of concizumab with NovoPen[®] 4 and in the use of eDiary.

Investigational medicinal product (IMP)

³ Not to be confused with the daily injected volume (~150 µL, depending on dose strength and body weight)

⁴ Non-investigational medicinal product (NIMP)

Protocol
Trial ID:NN7415-4255
UTN:U1111-1179-3872
EudraCT no.:2016-000614-29

~~CONFIDENTIAL~~

Date:	05 May 2017	Novo Nordisk
Version:	2	
Status:	Final	
Page:	34 of 124	

In case safety concerns meet the criteria (See section [12](#)) for putting enrolment of additional patients on hold, further enrolment in the trial will be halted. Dosing of patients on treatment may continue while further evaluation is made by the safety committee. In case of other safety concerns all available data will be evaluated by the DMC see Section [12.8.2](#).

5.3.1 Dose escalation

Bleeding episodes will be assessed during the trial both at scheduled visits and also between visits. The first 2 weeks of the treatment with concizumab 0.15 mg/kg is considered as a run-in period. Hence the bleeding episodes occurring during the first 2 weeks should not influence a dose escalation decision.

All spontaneous bleeding episodes (sBEs) are counted from 2 weeks after visit 2 (first-dose visit) until visit 16 (end-of-treatment visit), i.e. a total of 74 weeks. Dose-escalation will be based on the number of spontaneous, treated bleeding episodes in patients within preceding 12 weeks. However, before dose-escalation can occur, to ensure the safety of the patients, the investigator must take into account the full clinical picture the patient is presenting with and all available laboratory results, including coagulation parameters.

Dose 0.15 mg/kg:

When a sBE occurs, the investigator will determine if ≥ 3 sBEs have occurred within the preceding 12 weeks since visit 2+2weeks (including the current sBE). If yes, and if investigator deems it safe, the patient will have to be dose escalated from 0.15 to 0.20 mg/kg at the next scheduled visit. If the investigator judges that this visit is scheduled too late, he/she should contact the patient for an unscheduled visit.

Dose 0.20 mg/kg:

When an sBE occurs, the investigator will determine if ≥ 3 sBEs have occurred within the preceding 12 weeks (including the current sBE), counting only new sBEs from the beginning of the 0.20 mg/kg treatment period. If yes, and if investigator deems it safe, the patient will have to be dose escalated from 0.20 to 0.25 mg/kg at the next scheduled visit. If the investigator judges that this visit is scheduled too late, he/she should contact the patient for an unscheduled visit.

Dose 0.25 mg/kg:

Patients are not dose escalated further regardless of the number of sBEs. When an sBE occurs, the investigator will determine if ≥ 3 sBEs have occurred within the preceding 12 weeks (including the current sBE), counting only the new sBEs from the beginning of the 0,25mg/kg treatment period. If yes, then the patient must be discontinued from treatment due to lack of efficacy, see Section [6.4](#).

Since the patient may have to wait up to 8 weeks for the next scheduled visit (in the extension part), the possibility of dose escalation at unscheduled visits is necessary for the dose-escalation eliciting bleeding episode to occur soon after previous scheduled visit.

Protocol
 Trial ID: NN7415-4255
 UTN: U1111-1179-3872
 EudraCT no.: 2016-000614-29

CONFIDENTIAL

Date:
 Version:
 Status:
 Page:

05 May 2017 | **Novo Nordisk**
 2
 Final
 35 of 124

[figure not shown]

Figure 5–3 Dose escalation of concizumab for one individual patient

5.3.2 Treatment of bleeding episodes during the trial

Bleeding episodes (main part, extension part, and follow-up part):

Breakthrough bleeding episodes during the course of the trial will be treated at the discretion of the treating physician, with either turoctocog alfa/Novoeight[®] (rFVIII) (provided by Novo Nordisk) or other non-modified FVIII products (not provided by Novo Nordisk). Treatment dose is chosen at the discretion of the investigator. The patient can treat himself and then he must call the site. Bleeding episodes classified as severe must be recorded in the electronic case report form (eCRF) as serious adverse events (SAEs) see [Table 8–3](#). The bleeding episodes must be recorded in the eDiary.

FVIII prophylactic treatment (follow-up part):

During the follow-up part of the trial (i.e. from concizumab end-of-treatment visit to end-of-trial visit) patients will receive pre-trial FVIII medication at the discretion of the treating investigator, who will also choose dose levels. Only turoctocog alfa/NovoEight[®] will be provided by Novo Nordisk for this purpose.

5.3.3 Prohibited medication

- Treatment with anti-fibrinolytics (e.g. tranexamic acid, aminocaproic acid)
- Heparin, except for sealing of central venous access ports according to local practice
- Vitamin-K antagonists
- Direct oral anti-coagulants (DOACs)
- Modified FVIII products with extended half-life

Protocol
 Trial ID:NN7415-4255
 UTN:U1111-1179-3872
 EudraCT no.:2016-000614-29

~~CONFIDENTIAL~~

Date:	05 May 2017	Novo Nordisk
Version:	2	
Status:	Final	
Page:	36 of 124	

5.4 Treatment after discontinuation of trial product

When discontinuing trial products the patient should be switched to a suitable marketed product at the discretion of the investigator. The patient will not be provided with concizumab or FVIII (turoctocog alfa/NovoEight[®]) by Novo Nordisk after end of trial (visit 17).

5.5 Rationale for treatment

Concizumab is a monoclonal antibody and as such offers the possibility of s.c. administration. S.c. administration of an effective prophylactic drug has potential to reduce treatment burden significantly compared to the currently approved prophylactic drugs which have to be administered i.v.

The treatment period of 24 weeks (the main part of the trial) is considered necessary for providing data that allow demonstration of CPoC and to support decision-making regarding a phase 3 confirmatory trial. Dosing for an additional 52 weeks will provide valuable long-term efficacy and safety.

Breakthrough bleeding episodes may occur during prophylactic regimens with conventional FVIII replacement therapy. Therefore, it is expected that breakthrough bleeding episodes will also occur during prophylaxis with concizumab even if clinical proof of concept is demonstrated. Consequently turoctocog alfa (FVIII) will be provided by Novo Nordisk A/S in this trial for treatment of breakthrough bleeding episodes.

Patients are not obliged to use turoctocog alfa (FVIII) and can use their previously used FVIII concentrate for treatment of breakthrough bleeding episode. Novo Nordisk A/S will not provide or reimburse these products.

Please refer to the Investigator's Brochure for further information.

Protocol
Trial ID:NN7415-4255
UTN:U1111-1179-3872
EudraCT no.:2016-000614-29

~~CONFIDENTIAL~~

Date: 05 May 2017
Version: 2
Status: Final
Page: 37 of 124

Novo Nordisk

6 Trial population

6.1 Number of patients

Number of patients planned to be screened: 36

Number of patients planned to be started on trial product(s): 33

Number of patients planned to complete the trial: 30

Discontinued patients will not be replaced.

6.2 Inclusion criteria

For an eligible patient, all inclusion criteria must be answered “yes”.

1. Informed consent obtained before any trial-related activities. Trial-related activities are any procedures that are carried out as part of the trial, including activities to determine suitability for the trial.
2. Male patients aged ≥ 18 years at the time of signing informed consent, diagnosed with severe haemophilia A (FVIII activity $<1\%$), based on medical records or results at screening.
3. For patients being treated on-demand with FVIII replacement therapy, a minimum of six documented and treated bleeding episodes during the 24 weeks (or twelve bleeds during 52 weeks) prior to screening.

6.3 Exclusion criteria

For an eligible patient, all exclusion criteria must be answered “no”.

1. Known or suspected hypersensitivity to trial product(s) or related products.
2. Previous participation in this trial. Participation is defined as signed informed consent.
3. Participation in any clinical trial of an approved or non-approved investigational medicinal product within the last 30 days or 5 half-lives (whichever is longer) from the last drug administration before screening.
4. Any disorder, which in the investigator’s opinion might jeopardise patient’s safety or compliance with the protocol.
5. Known inherited or acquired bleeding disorder other than haemophilia A.
6. Major surgery conducted within one month prior to the initiation of trial activities or major surgery planned to occur during the trial.
7. Previous history of thromboembolic disease. Current clinical signs of thromboembolic disease, or patients who in the judgement of the investigator are considered at high risk of thromboembolic events.

Protocol
 Trial ID: NN7415-4255
 UTN: U1111-1179-3872
 EudraCT no.: 2016-000614-29

~~CONFIDENTIAL~~

Date:	05 May 2017	Novo Nordisk
Version:	2	
Status:	Final	
Page:	38 of 124	

8. Mental incapacity, unwillingness to cooperate or language barrier precluding adequate understanding and cooperation.
9. Patients who, at screening, have a significant infection or known systemic inflammatory condition which require systemic treatment according to the investigator's judgement.
10. Hepatic dysfunction defined as elevated liver transaminases (ALT) >3 times the upper limit of normal laboratory reference ranges at screening.
11. Renal impairment defined as estimated glomerular filtration rate (eGFR) ≤ 60 mL/min/1.73m² based on serum creatinine measured at screening or evidence of renal damage.
12. Platelet count $\leq 100 \times 10^9/L$ at screening.
13. Fibrinogen level < the lower limit of normal at screening
14. Presence of inhibitors (neutralising antibodies) to Factor VIII (≥ 0.6 Bethesda Units) at screening measured by the Nijmegen method.
15. History of inhibitors towards FVIII based on investigator's knowledge or documentation in available medical records.

6.4 Criteria for premature discontinuation of trial product

The patient may be prematurely discontinued from trial product at the discretion of the investigator due to a safety concern.

The patient must be prematurely discontinued from trial product if the following applies:

1. Included in the trial in violation of the inclusion and/or exclusion criteria
2. Simultaneous participation in another clinical trial of an approved or non-approved investigational medicinal product.
3. Incapacity or unwillingness to follow the trial procedures
4. Anaphylactic reaction
5. Thromboembolic event
6. Event of disseminated intravascular coagulation (DIC)
7. Development of inhibitors to Factor VIII (≥ 0.6 BU)
8. Lack of efficacy due to neutralising antibodies towards concizumab
9. Lack of efficacy defined as ≥ 3 treated sBEs within the previous 12 weeks in patients being treated with the highest dose level (0.25 mg/kg) of concizumab.

See Section [8.1.4](#) for procedures to be performed for patients discontinuing trial product prematurely.

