p	Patient should be dose escalated at next scheduled visit if he experiences ≥3 spontaneous bleeding episodes within the preceding 12 weeks of treatment with concizumab. If investigator judges that next scheduled visit is too late an unscheduled visit should be performed for dose escalation.
q	Home treatment training must take place at visit 2 at the latest and whenever needed afterwards. Home treatment training comprises handing out of Direction for Use (DFU), training in administration of concizumab with NovoPen®4, turoctocog alfa and data entry in eDiary. Further the patients will be trained in recognition of signs/symptoms of thrombosis.

Protocol
 Trial ID:NN7415-4255
 UTN:U1111-1179-3872
 EudraCT no.:2016-000614-29

~~CONFIDENTIAL~~

Date:	05 May 2017	Novo Nordisk
Version:	2	
Status:	Final	
Page:	21 of 124	

3 Background information and rationale for the trial

The trial will be conducted in compliance with this protocol, International Conference on Harmonisation Good Clinical Practice (ICH GCP)¹ and applicable regulatory requirements, and in accordance with the Declaration of Helsinki² and ISO 14155³.

In this document, the term investigator refers to the individual responsible for the overall conduct of the clinical trial at a trial site.

The International Non-Proprietary Names for Pharmaceutical Substances (INN) name of the active pharmaceutical ingredient is concizumab (synonyms used during early development are NNC0172-2021, anti-TFPI, NN7415 or mab2021). Throughout this document “concizumab” is used as the name of the trial drug.

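### The mandatory lack-of-efficacy stop at 0.25 mg/kg is counted with a restart in 5.3.1 and without one in 6.4(9), so bleeds from 0.20 mg/kg can meet it on arrival; Table 2-2 note p has a related gap for escalation

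*Protocol*

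**What the plan says.** All passages below are from version 2 of the protocol (05 May 2017).

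**Section 5.3.1, escalation.** The introduction bases escalation on treated spontaneous bleeds: "Dose-escalation will be based on the number of spontaneous, treated bleeding episodes in patients within preceding 12 weeks". It sets aside the run-in: "Hence the bleeding episodes occurring during the first 2 weeks should not influence a dose escalation decision". For the step from 0.20 to 0.25 mg/kg the count restarts, "counting only new sBEs from the beginning of the 0.20 mg/kg treatment period".

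**Section 5.3.1, stop at 0.25 mg/kg.** Three or more spontaneous bleeding episodes (sBEs) in 12 weeks lead to discontinuation, "counting only the new sBEs from the beginning of the 0,25mg/kg treatment period". This block says sBEs without the word treated, and it refers the reader to 6.4.

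**Section 6.4.** The list opens with "The patient must be prematurely discontinued from trial product if the following applies". Criterion 9 is three or more "treated sBEs within the previous 12 weeks in patients being treated with the highest dose level (0.25 mg/kg) of concizumab". It contains no restart and no reference back to 5.3.1.

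**Table 2-2, note p.** Escalation follows three or more "spontaneous bleeding episodes within the preceding 12 weeks of treatment with concizumab". The note has no restart, no run-in exclusion and no treated condition. The design rationale in 5.2 summarises the trigger in the same short form.

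**The concern.** A patient reaches 0.25 mg/kg because he had at least three sBEs within 12 weeks on 0.20 mg/kg. If the 12-week window in 6.4(9) runs back across the dose change, those same bleeds can satisfy the stop before the new dose has been tried. Under 5.3.1 they do not count.

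The difference affects patients and data. Permanent discontinuation leads to withdrawal from the trial (8.1.4), and discontinued patients are not replaced (6.6). The primary proof-of-concept criterion uses only time on the end dose (section 17), and only data before discontinuation enter the inference (17.3). A patient stopped on arrival would add almost no time at 0.25 mg/kg, and his bleeds on 0.20 mg/kg would fall outside the end-dose period. With about 30 patients behind the analysis, each such case counts.

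Note p raises a similar but separate question for escalation: read alone, it lets the bleeds that led to 0.20 mg/kg support the next step as well.

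**Working it through.** **The plan's own figure.** Section 5.3.1 gives a counting period of 74 weeks, from two weeks after visit 2 to visit 16: 76 − 2 = 74. This agrees.

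**The wordings side by side.**

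| | 5.3.1 | 6.4(9) | Table 2-2 note p |
|---|---|---|---|
| Governs | escalation and stop | stop | escalation |
| Restart at new dose | yes | no | no |
| Run-in excluded | yes | not stated | no |
| Treated bleeds only | introduction yes; dose blocks do not repeat it | yes | no |

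Version 1 has no stop rule at 0.25 mg/kg, so this is not a difference between versions. The conflict lies inside version 2.

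**Worked case.** Suppose 0.20 mg/kg starts at week 8, treated sBEs occur at weeks 9, 10 and 11, and 0.25 mg/kg starts at the week 12 visit. Under 6.4(9) the window is weeks 0 to 12, and the bleeds on 0.20 mg/kg alone give 3, so the stop is met. Under 5.3.1 the count on arrival is 0.

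**How often this would happen.** The protocol gives no rate of treated sBEs on concizumab, so a range was assumed.

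- Inputs from the protocol: 76 weeks of treatment; counting from week 2; trigger of three sBEs within 12 weeks with the 5.3.1 restart; scheduled visits at weeks 4, 8, 12, 16, 20, 24 and then 8-weekly to week 72 (8.1.9.4 to 8.1.10.2).
- Assumptions: treated sBEs follow a Poisson process at a constant rate λ per year, so a patient has on average λ × 76/52 over treatment; escalation occurs at the next scheduled visit; 40,000 simulated patients per rate.
- Share meeting 6.4(9) on arrival = arrivals at 0.25 mg/kg with at least 3 sBEs in the preceding 12 weeks, divided by all arrivals at 0.25 mg/kg.

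| Treated sBEs per year (assumed) | 4 | 6 | 12 | 20 | 30 |
|---|---|---|---|---|---|
| All arrivals at 0.25 mg/kg: already meet 6.4(9) | 68% | 74% | 89% | 98% | 99.8% |
| Arrivals by week 24: already meet 6.4(9) | 97% | 97.5% | 98% | 99% | 99.8% |
| Either group under 5.3.1 | 0% | 0% | 0% | 0% | 0% |
| Arrivals at 0.20 mg/kg: already meet note p for the next step | 70% | 76% | 90% | 97% | 99.5% |

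Repeat runs moved the 4-per-year entry in the first row between about 67% and 69%. If escalation takes place at once at an unscheduled visit, the first two rows become 100%. The note p row leaves out run-in bleeds, which note p itself would count, so it is if anything too low.

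**How many patients arrive.** In the same simulation 0.5%, 2.9% and 30.5% of all patients reach 0.25 mg/kg by week 24 at 4, 6 and 12 treated sBEs per year. Of 33 treated patients that is 33 × 0.005 = 0.2, 33 × 0.029 = 1.0 and 33 × 0.305 = 10.1. These counts assume that a higher dose does not reduce bleeding.

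**The case against.** The best defence is that 5.3.1 contains the whole rule and the other passages are abbreviations of it. It states the restart for the stop in terms and then points to 6.4 as the same stop. The procedures for visits 4 to 8, 9, 10 and 11 to 15 all send the investigator to 5.3.1 for escalation. A careful site reading both sections together would probably apply the restart. Escalating a patient only to stop him the same day would also be an odd intention to attribute to the sponsor.

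Much of this stands. A reader might infer that patients reaching 0.25 mg/kg will in fact be stopped on arrival, and the documents do not support that. It follows only from applying 6.4(9) alone, and even then not always, because early bleeds can leave the 12-week window before a late visit. Nor can note p trigger the stop, since it concerns escalation only. A second escalation without a new bleed requires note p to be used in isolation: 5.3.1 begins each assessment with a new sBE and requires the investigator to judge the step safe after weighing the clinical picture and coagulation results.

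The mismatch over treated bleeds is minor. The introduction to 5.3.1 can be read as covering the dose blocks beneath it, although that sentence speaks of escalation and not of the stop.

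The defence does not remove the conflict in 6.4(9). That criterion stands under a mandatory heading, gives its own complete definition and does not refer to 5.3.1. A site or monitor checking discontinuation criteria would turn to 6.4.

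**Conclusion.** The contradiction is real and should be corrected: one mandatory stop has two definitions that give opposite answers for the same patient on the same day. Applied literally, 6.4(9) would be met on arrival by roughly 68% to 99.8% of patients reaching 0.25 mg/kg at a scheduled visit, and by about 97% or more of those arriving by week 24, against none under 5.3.1. These shares rest on assumed constant rates of 4 to 30 treated sBEs per year and on escalation at scheduled visits. The contradiction itself depends on no rate. The omissions in note p are a second, smaller inconsistency limited to escalation.

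A reader might infer that the primary bleeding rate is therefore biased by a known amount. That is not shown. The choice of wording changes who contributes time at 0.25 mg/kg, but its effect on the estimated rate, the confidence limit or the power has not been calculated. It depends on how many patients escalate and how they would have bled on the higher dose.

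**What to change.** Reconcile 5.3.1, 6.4(9) and Table 2-2 note p, with the summary in 5.2, into one identical counting rule. It should settle three things: whether the count restarts at each dose, whether run-in bleeds count, and whether all sBEs or only treated ones count. Alternatively, keep a single definition and have 6.4(9) and note p refer to it. Which clinical rule applies is the sponsor's decision; the passages cannot all stand as written.

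In the analysis, take each patient's end dose from the dose actually given and not from a re-application of the counting rule, so that the primary data set reflects what happened even where sites read the rule differently.

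The cost is amendment wording and a clarification to sites. No additional data are needed.

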6.5 Withdrawal from trial

The patient may withdraw consent at will at any time.

See Section [8.1.5](#) for procedures to be performed for patients withdrawing consent.

Protocol
Trial ID:NN7415-4255
UTN:U1111-1179-3872
EudraCT no.:2016-000614-29

~~CONFIDENTIAL~~

Date: 05 May 2017
Version: 2
Status: Final
Page: 39 of 124

Novo Nordisk

6.6 Patient replacement

Patients who discontinue trial product prematurely will not be replaced.

6.7 Rationale for trial population

The most important reason for choosing the trial population, haemophilia A without inhibitors, is that there is a significant unmet medical need in this patient population for a treatment option which reduces the burden associated with the current care, including small volume s.c. administration instead of i.v. Finally, the trial population reflects the patient population that will be selected in a potential subsequent phase 3 trial in which the efficacy and safety of concizumab is to be confirmed.

Protocol
 Trial ID:NN7415-4255
 UTN:U1111-1179-3872
 EudraCT no.:2016-000614-29

~~CONFIDENTIAL~~

Date:	05 May 2017	Novo Nordisk
Version:	2	
Status:	Final	
Page:	40 of 124	

7 Milestones

Planned duration of recruitment period first patient first visit – last patient first visit (FPFV-LPFV):
 4 months

Planned FPFV:	16-Aug-2017
Planned FPFT:	30-Aug-2017
Planned LPFV:	16-Dec-2017
Planned LPLV:	11-Sep-2019

The total duration of concizumab treatment in the trial is 76 weeks for an individual patient enrolled in the trial for concizumab treatment at visit 2.

End of trial is defined as last patient last visit (LPLV).

Recruitment:

The screening and enrolment rate will be followed closely via the interactive web response system (IWRS) in order to estimate when to stop screening. All investigators will be notified immediately when the recruitment period ends, after which no further patients may be screened and the IWRS will be closed for further screening. All patients screened during the recruitment period and found eligible for enrolment can be enrolled within the timelines specified in the flow chart (see Section [2](#)).

Trial registration:

Information about the trial will be disclosed at clinicaltrials.gov, novonordisk-trials.com and clinicaltrials.com. According to the Novo Nordisk Code of Conduct for Clinical Trial Disclosure, [how-we-disclose-trial-information](#)⁸, it will also be disclosed according to other applicable requirements such as those of the International Committee of Medical Journal Editors (ICMJE)⁹, the Food and Drug Administration Amendment Act (FDAAA)¹⁰, European Commission Requirements^{11, 12} and other relevant recommendations or regulations¹³. If a patient requests to be included in the trial via the Novo Nordisk e-mail contact at these web sites, Novo Nordisk may disclose the investigator's contact details to the patient. As a result of increasing requirements for transparency, some countries require public disclosure of investigator names and their affiliations.

Primary Completion Date (PCD) is the last assessment of the primary endpoint, and is for this protocol Last Patient First Treatment LPFT (visit2) + 24 weeks (i.e. last patient visit 9) If the last patient is withdrawn early the PCD is the date when the last patient would have completed visit 9. The PCD determines the deadline for results disclosure at ClinicalTrials.gov according to FDAAA.¹⁰

Protocol
 Trial ID: NN7415-4255
 UTN: U1111-1179-3872
 EudraCT no.: 2016-000614-29

CONFIDENTIAL

Date:
 Version:
 Status:
 Page:

05 May 2017 | **Novo Nordisk**
 2
 Final
 41 of 124

8 Methods and assessments

Assessments to be performed at the scheduled and at unscheduled visits in this trial are described in this section and in the trial flow chart (section 2).

[figure not shown]

Figure 8-1 Overview of visit structure in explorer™5

